6.2 Exclusion Criteria

- 1) **Medical Conditions**
 - a) Women who are breastfeeding
 - b) Any major surgery within 4 weeks of study drug administration. Note: Participants must have recovered from the effects of major surgery or significant traumatic injury at least 14 days before the first dose of study drug.
- 2) **Medical History and Concurrent Diseases**
 - a) For Part 1C only, participants who experienced Grade 3 or above infusion-related reactions from prior EGFR inhibiting therapy.
 - b) Participants with active, known or suspected autoimmune disease.
 - (1) Participants with atopic dermatitis, well controlled asthma and/or mild allergic rhinitis (seasonal allergies) are eligible
 - (2) Participants with the following disease conditions are also eligible:
 - (a) Vitiligo
 - (b) Type 1 diabetes mellitus on stable conditions under insulin treatment
 - (c) Residual hypothyroidism due to autoimmune condition only requiring hormone replacement
 - (d) Euthyroid participants with a history of Graves' disease (participants with suspected autoimmune thyroid disorders must be negative for thyroglobulin and thyroid peroxidase antibodies and thyroid stimulating Ig prior to the first dose of study drug(s).

(3) The pathogenesis of psoriasis has been linked to the activity of NK cells and therefore participants with psoriasis with any degree of severity are excluded from this study.

- c) Participants with a condition requiring systemic treatment with either corticosteroids (> 10 mg daily prednisone equivalent) or other immunosuppressive medications within 14 days of study treatment. Note: Inhaled or topical steroids, and adrenal replacement steroid doses > 10 mg daily prednisone equivalent, are permitted in the absence of active autoimmune disease.
- d) **Not applicable per protocol revision 02:** Known history of positive test for human immunodeficiency virus (HIV) or known acquired immunodeficiency syndrome (AIDS). NOTE: Testing for HIV must be performed at sites where mandated locally.
- e) Participants with concomitant second malignancies (except adequately treated nonmelanomatous skin cancers or in situ bladder, breast, or cervical cancers) are excluded unless a complete remission was achieved at least 2 years prior to study entry, and no additional therapy is required or anticipated to be required during the study period. However, participants with concomitant malignancies that do not require treatment and are clinically stable and anticipated to be followed in an active surveillance manner for the next 12 months may be eligible, upon agreement with the medical monitor. Treatment should not be required at timing of consent and not be expected to be needed not only for the concurrent malignancy, but also for complications caused by it. The investigator should inform the participant that the study treatment is not intended and not expected to be considered as treatment for the concurrent malignancy.
- f) Participants with serious or uncontrolled medical disorders.
- g) Participants with history of life-threatening toxicity related to prior immune therapy (eg. anti-CTLA-4 or anti-PD-1/PD-L1 treatment or any other antibody or drug specifically targeting T-cell co-stimulation or immune checkpoint pathways) except those that are unlikely to re-occur with standard countermeasures (eg. hormone replacement after adrenal crisis).
- h) Prior organ or tissue allograft
- i) Uncontrolled or significant cardiovascular disease including, but not limited to any of the following:
 - i) Myocardial infarction or stroke/transient ischemic attack within the past 6 months
 - ii) Uncontrolled angina within the past 3 months
 - iii) Any history of clinically significant arrhythmias (such as ventricular tachycardia, ventricular fibrillation, or torsades de pointes)
 - iv) History of other clinically significant heart disease (e.g., cardiomyopathy, congestive heart failure with New York Heart Association functional classification III to IV ([Appendix 9](#))).
 - v) Cardiovascular disease-related requirement for daily supplemental oxygen therapy
 - vi) QT interval corrected for heart rate using Fridericia's formula (QTcF) prolongation > 480 msec, except for right bundle branch block
 - vii) History of myocarditis regardless of etiology
- j) History of or with active interstitial lung disease or pulmonary fibrosis

k) History of chronic hepatitis as evidenced by the following:

- (a) Positive test for hepatitis B surface antigen
- (b) Positive test for qualitative hepatitis C viral load by PCR
- (c) Participants with positive hepatitis C antibody and negative quantitative hepatitis C by PCR are eligible. History of resolved hepatitis A virus infection is not an exclusion criterion.
- (d) Additional testing or substitute testing per institutional guidelines to rule out infection is permitted

l) Evidence of active infection that requires systemic antibacterial, antiviral, or antifungal therapy ≤ 7 days prior to the first dose of study drug (except for viral infections that are presumed to be associated with the underlying tumor type required for study entry).

m) Receipt of non-oncology vaccines containing live virus for prevention of infectious diseases within 30 days prior to first dose of study drug.

n) Any significant acute or chronic medical illness which would interfere with study treatment or follow-up.

o) Any serious or uncontrolled medical disorder that, in the opinion of the investigator, may increase the risk associated with study participation or study drug administration, impair the ability of the participant to receive protocol therapy, or interfere with the interpretation of study results.

p) Previous SARS-CoV-2 infection within 10 days for mild or asymptomatic infections or 20 days for severe/critical illness prior to C1D1.

- i) Acute symptoms must have resolved and based on investigator assessment in consultation with the medical monitor, there are no sequelae that would place the participant at a higher risk of receiving study treatment.

q) Previous SARS-CoV-2 vaccine within 14 days of C1D1.

r) Known HIV positive with an AIDS defining opportunistic infection within the last year or a current CD4 count < 350 cells/ μ L. Participants with HIV are eligible if:

- ◆ they have received antiretroviral therapy (ART) for at least 4 weeks prior to treatment assignment as clinically indicated while enrolled on study
- ◆ they continue on ART as clinically indicated while enrolled on study
- ◆ CD4 counts and viral load are monitored per standard of care by a local health care provider

NOTE: Testing for HIV must be performed at sites where mandated locally.
HIV-positive participants must be excluded where mandated locally.

s) Leptomeningeal metastases

3) Prior/Concomitant Therapy

- a) Cytotoxic agents, unless at least 4 weeks have elapsed from last dose of prior anti-cancer therapy and initiation of study therapy.
- b) Non-cytotoxic agents, unless at least 4 weeks or 5 half-lives (whichever is shorter) have elapsed from the last dose of prior anti-cancer therapy and the initiation of study therapy. agents.

- c) Prior immune therapy treatments, unless at least 4 weeks or 5 half-lives (whichever is shorter) have elapsed from the last dose of immune therapy and initiation of study therapy.
- d) Prior participation in anti-NKG2A clinical study
- e) Treatment with botanical preparations (eg herbal supplements or traditional Chinese medicines) intended for general health support or to treat the disease under study within 2 weeks prior to randomization/treatment. Refer to [Section 7.7.1](#) for prohibited therapies.
- f) SCCHN participants to be enrolled in Part 1C:
 - i) Previous treatment with cetuximab, unless it was received in the locally advanced setting and did not have progressive disease for at least 4 months of treatment. Use of cetuximab in the R/M setting is an exclusion criteria, regardless of response.
 - ii) Prior Grade 3 or 4 cetuximab related IRR
 - iii) Active severe acne or skin infection
 - iv) Allergy to galactose-alpha-1 and 3-galactose (alpha-gal)
 - v) Hypomagnesemia, unless imbalance is corrected and a follow up test demonstrates normal magnesium levels

4) Physical and Laboratory Test Findings

- a) WBC < 2,000/ μ L
- b) Neutrophils < 1500/ μ L
- c) Platelets < 100×10^3 / μ L
- d) Hemoglobin < 9.0 g/dL
- e) Serum creatinine > $1.5 \times$ ULN, unless creatinine clearance ≥ 40 mL/min (measured or calculated using the Cockcroft-Gault formula)
- f) AST/ALT: > $3.0 \times$ ULN
- g) Total bilirubin > $1.5 \times$ ULN (except participants with Gilbert Syndrome who must have a total bilirubin level of < $3.0 \times$ ULN).

5) Allergies and Adverse Drug Reaction

- a) History of allergy, hypersensitivity, or serious adverse reaction to monoclonal antibodies or related compounds
- b) History of allergy or hypersensitivity to study drug components

6) Other Exclusion Criteria

- a) Prisoners or participants who are involuntarily incarcerated. (Note: under certain specific circumstances and only in countries where local regulations permit, a person who has been imprisoned may be included or permitted to continue as a participant. Strict conditions apply and Bristol Myers Squibb approval is required.)
- b) Participants who are compulsorily detained for treatment of either a psychiatric or physical (eg, infectious disease) illness.

Eligibility criteria for this study have been carefully considered to ensure the safety of the study participants and that the results of the study can be used. It is imperative that participants fully meet all eligibility criteria.

6.3 Lifestyle Restrictions

Participants in Part 1C should be advised to avoid sun exposure. Participants should wear sunscreen and hats and limit sun exposure during treatment and for 2 months after the last dose of cetuximab.

6.4 Screen Failures

Screen failures are defined as participants who consent to participate in the clinical study but who are not subsequently entered in the study/included in the analysis population. A minimal set of screen failure information is required to ensure transparent reporting of screen failure participants, to meet the Consolidated Standards of Reporting Trials (CONSORT) publishing requirements, as applicable, and to respond to queries from regulatory authorities. Minimal information includes date of consent, demography, screen failure details, eligibility criteria, and any serious AEs.

6.4.1 Retesting During Screening or Lead-In Period

Participant Re-enrollment: This study permits the re-enrollment of a participant that has discontinued the study as a pre-treatment failure (ie, participant / has not been treated). If re-enrolled, the participant must be re-consented

Retesting of laboratory parameters and/or other assessments during the extended screening period will be permitted (in addition to any parameters that require a confirmatory value). The most current result prior to treatment assignment is the value by which study inclusion will be assessed, as it represents the participant's most current, clinical state.

Laboratory parameters and/or assessments that are included in [Table 2-1](#), Screening Procedural Outline may be repeated in an effort to find all possible well-qualified participants. Consultation with the Medical Monitor may be needed to identify whether repeat testing of any particular parameter is clinically relevant.

Testing for asymptomatic SARS-CoV-2 infection by RT-PCR or viral antigen is not required. However, some participants may develop suspected or confirmed symptomatic SARS-CoV-2 infection, or be discovered to have asymptomatic SARS-CoV-2 infection during the screening period. In such cases, subjects may be considered eligible for the study after meeting all inclusion/exclusion criteria related to active infection, and after meeting the following criteria:

- At least 10 days (20 days for severe/critical illness) have passed since symptoms first appeared or positive RT-PCR or viral antigen test result, and
- At least 24 hours have passed since last fever without the use of fever-reducing medications, and
- Acute symptoms (eg, cough, shortness of breath) have resolved, and
- In the opinion of the investigator, there are no SARS-CoV-2 infection sequelae that may place the participant at a higher risk of receiving investigational treatment.
- In the instance of a SARS-CoV-2 infection during screening, the screening period may be extended beyond the protocol-specified timeframe with Medical Monitor approval. Any

screening tests already performed which could potentially be affected by the SARS-CoV-2 infection or its complications on an individual basis and agreed upon with the Medical Monitor (eg, safety labs, oxygen saturation, chest CT scan) should be repeated.

7 TREATMENT

Study treatment is defined as any investigational treatment(s), marketed product(s), placebo or medical device intended to be administered to a study participant according to the study randomization or treatment allocation

Study treatment includes both Investigational [Medicinal] Product (IP/IMP) and Non-investigational [Medicinal] Product (Non-IP/Non-IMP) and can consist of the following:

- BMS-986315
- Nivolumab
- Cetuximab

An investigational product, also known as investigational medicinal product in some regions, is defined a pharmaceutical form of an active substance or placebo being tested or used as a reference in a clinical study, including products already with a marketing authorization but used or assembled (formulated or packaged) differently than the authorized form, or used for an unauthorized indication, or when used to gain further information about the authorized form.

Drugs used in this open-label study qualify as IPs. Their description and storage information are described in [Table 7-1](#). Please refer to the Pharmacy Manual for additional information.

Table 7-1: Study treatments for CA047004

Product Description / Class and Dosage Form	Potency	IP/Non-IMP	Blinded or Open Label	Packaging / Appearance	Storage Conditions (per label)
BMS-986315	120mg/mL	IP	Open Label	Kit	Refer to Product Label
Nivolumab	10 mg/mL	IP	Open Label	Kit	Refer to Product Label
Cetuximab	100 mg/50mL, 200 mg/100 mL & various strengths	IP	Open Label	Kit	Refer to Product Label

Abbreviations: IP: Investigational Product

Other medications used as support or escape medication for preventative, diagnostic, or therapeutic reasons, as components of the standard of care for a given diagnosis, may be considered as non-investigational products.

7.1 Treatments Administered

The dosing schedule for each IP is detailed below in Table 7.1-1 for all study parts. Planned dose levels may be modified (eg, change in administration schedule) based upon evaluation of all available safety, PK, and pharmacodynamic data.

All participants will be monitored continuously for AEs while on study treatment. Treatment modifications (eg, dose delay, reduction, re-treatment, or discontinuation) will be based on specific laboratory and AE criteria, as described in [Section 7.4](#). All participants treated in Part 1C should receive pre-medication as described in [Section 7.4.2.3](#).

Table 7.1-1: Selection and Timing of Dose^a

Study Treatment	Unit dose strength(s)/Dosage level(s)	Dosage formulation Frequency of Administration	Route of Administration
BMS-986315	80, 200, 600, 1200, and 2400 mg	Q4W	IV
Nivolumab	480mg	Q4W	IV
Cetuximab	500mg/m ²	Q2W	IV

Abbreviations: Q4W = every 4 weeks; Q2W = every 2 weeks; IV = intravenous

^aAdditional doses may be explored.

7.2 Method of Treatment Assignment

During the screening visit, the investigative site will call into the enrollment option of the Interactive Response Technology (IRT) designated by BMS for assignment of a 5-digit participant number that will be unique across all sites. Enrolled participants, including those not dosed, will be assigned sequential participant numbers starting with 00001, (e.g., 00001, 00002, 00003....00010). The patient identification number (PID) will ultimately be comprised of the site number and participant number. For example, the first participant screened (i.e., enrolled) at site number 1, will have a PID of 0001 00001. Once it is determined that the participant meets the eligibility criteria following the screening visit, the investigative site will call the IRT to assign the participant into the open dose panel.

Participants will not be replaced if they are discontinued from the study secondary to an adverse event unless the adverse event can be determined to be unrelated to treatment. All eligible participants will be initially assigned to Part 1A (dose escalation of BMS-986315 monotherapy) until the decision is made to escalate to the third dose cohort. Subsequently, treatment in Part 1B and Part 1C can be initiated, and dose escalation in the 3 parts will occur in parallel. That is, Part 1B and Part 1C can be initiated when at least 2 dose levels (the current and 1 higher) in Part 1A have cleared the DLT period in accordance with dose escalation rules, after which dose escalation in Part 1A, Part 1B, and Part 1C will proceed in parallel. Treatment assignments will alternate between all open study parts, with consecutively treated participants assigned to different parts, through IRT, based on cohort availability and inclusion criteria.

In addition, participants enrolled in monotherapy or combination pharmacodynamic cohorts will be assigned to dose levels that are already established as safe based on data coming from the

corresponding dose escalation cohort (see [Section 5.1](#)). PD cohort enrollment will take place in Part 1A, Part 1B, and Part 1C. Within each PD cohort, participants will be further assigned to either a CD8/HLA-E positive sub-cohort (biomarker positive), or a CD8/HLA-E negative sub-cohort (biomarker negative) based on the results of biomarker expression analysis.

7.3 Blinding

This is a non-randomized open-label study. The specific treatment to be taken by a participant will be assigned using an Interactive Response Technology (IRT). The site will contact the Interactive Response System prior to the start of study treatment administration for each participant. The site will record the treatment assignment on the applicable case report form, if required.

Designated staff of Bristol Myers Squibb Research & Development may obtain the treatment codes prior to database lock to facilitate the bioanalytical analysis of PK samples and immunogenicity. A bioanalytical scientist in the Bioanalytical Sciences department of Bristol Myers Squibb Research & Development (or a designee in the external central bioanalytical laboratory) will have access to the treatment assignments in order to minimize unnecessary bioanalytical analysis of samples.

7.4 Dosage Modification

Intra-participant dose escalation/reduction of BMS-986315 or nivolumab is not permitted in this study in order to allow better evaluation of the safety and efficacy at individual dose levels and schedules. No dose reductions of BMS-986315 or nivolumab will be allowed. Cetuximab dose may be reduced due to toxicity as described below.

7.4.1 Dose Delays Due to Toxicity

Participants who experience the following must have all study drug(s) withheld:

- Potential DLTs, until DLT relatedness is defined.
- Select AEs and laboratory abnormalities:
 - \geq Grade 1 pneumonitis
 - \geq Grade 2 abnormality in AST, ALT or total bilirubin
 - \geq Grade 2 creatinine increased
 - \geq Grade 2 diarrhea or colitis
 - \geq Grade 2 neurological AE
 - Grade 2 myocarditis
 - AE, laboratory abnormality, or concurrent illness that, in the judgment of the Investigator, warrants delaying study drug administration.
 - For SCCHN participants in Part 1C: Grade 3 or 4 acneiform rash
 - Confirmed SARS-CoV-2 infection

Criteria for participants who are required to permanently discontinue both study drugs is listed in [Section 8](#). Participants not meeting guidelines for permanent discontinuation will be permitted to

resume therapy based on the criteria specified below in [Section 7.4.2](#). Participants eligible to resume study therapy will resume study therapy at the nominal treatment visit following their last received study medication dose.

The end of cycle tumor assessments, such as computed tomography (CT), magnetic resonance imaging (MRI), or positron emission tomography (PET), will continue on a Q8W schedule relative to the participant's first dose, regardless of any treatment delay incurred

7.4.2 Criteria to Resume Treatment

Subsequent dosing with study therapy may resume once drug-related non DLT AEs resolve to Grade 1 or baseline. Participants experiencing AEs not meeting criteria for permanent discontinuation as outlined in [Section 8](#) may resume treatment with study medication under the following criteria:

Participants may resume treatment with study drug when the drug-related AE(s) resolve to Grade 1 or baseline value, with the following exceptions:

- Participants may resume treatment in the presence of Grade 2 fatigue
- Participants who have not experienced a Grade 3 drug-related skin AE may resume treatment in the presence of Grade 2 skin toxicity
- Participants with Grade 2 uveitis, episcleritis, iritis, eye pain or blurred vision not meeting DLT criteria ([Section 5.1.3](#)) must resolve to baseline prior to resuming study therapy
- For participants with Grade 2 AST, ALT, or total bilirubin elevations, dosing may resume when laboratory values return to baseline, and management with corticosteroids, if needed, is complete
- Participants with combined AST/ALT and total bilirubin values meeting DLT criteria ([Section 5.1.3](#)) should have treatment permanently discontinued.
- Drug-related pulmonary toxicity, diarrhea or colitis must have resolved to baseline before treatment is resumed. Participants with persistent Grade 1 pneumonitis after completion of a steroid taper over at least 1 month may be eligible for retreatment if discussed with and approved by BMS Medical Monitor (or designee).
- Participants with SCCHN in Part 1C may resume treatment in the presence of Grade 2 cetuximab-induced acneiform rash. Please see [Section 7.4.2.1](#) for management and dose reduction guidelines.
- Participants with confirmed SARS-CoV-2 infection may resume treatment after 1) at least 10 days (20 days for severe/critical illness) have passed since symptoms first appeared, positive RT-PCR test result, or positive RT-PCR viral antigen test result, 2) resolution of acute symptoms (including at least 24 hours has passed since last fever without fever-reducing medications), 3) evaluation by the Investigator with confirmation that there are no sequelae that would place the participant at a higher risk of receiving investigational treatment, and 4) consultation by the medical monitor. For suspected cases, treatment may also resume if SARS-CoV-2 infection is ruled-out and other criteria to resume treatment are met.
 - Prior to re-initiating on-study treatment in a participant with a dosing delay lasting 8 weeks due to SARS-CoV-2 infection, the medical monitor/designee must be consulted

Participants with drug-related endocrinopathies adequately controlled with only physiologic hormone replacement may resume treatment after consultation with the BMS Medical Monitor (or designee).

7.4.2.1 *Management of Cetuximab-Induced Acneiform Rash*

Participants with SCCHN in Part 1C must have treatment withheld if diagnosed with Grade 3 or 4 dermatologic toxicity or acneiform rash. Treatment may be resumed when the event has improved to Grade 2, with dose management as described below. If Grade ≥ 3 rash does not resolve to Grade ≤ 2 within 14 days of interruption of cetuximab treatment and despite optimal supportive care, the patient should not receive any further treatment with cetuximab. BMS-986315 treatment may be continued upon discussion between the investigator and the sponsor.

The recommendations for management are as follows:

General/Prevention:

- Grade 1 rash: mild rash may not need treatment. However, if treatment is considered necessary, topical hydrocortisone (1% or 2.5%) cream and/or clindamycin 1% gel can be used.
- Grade 2 rash: relief from major symptoms caused by Grade 2 skin-related adverse events should be achieved by a combination of local and systemic therapies including systemic antibiotics (e.g., doxycycline or minocycline), topical treatment (e.g., hydrocortisone 2.5% cream, clindamycin 1% gel, pimecrolimus 1% cream), antihistamines (e.g., diphenhydramine). Oral corticosteroids will not be allowed for the management of Grade 1 and 2 rash.
- Grade 3 (or greater) rash: may be treated in a manner similar to Grade 2 rash. In the event of Grade ≥ 3 rash, treatment with cetuximab should be paused until recovery Grade ≤ 2 . Treatment should be resumed at a reduced dose (see below). If Grade ≥ 3 rash does not resolve to Grade ≤ 2 within 14 days of stopping cetuximab treatment and despite optimal supportive care, the patient should not receive any further treatment with cetuximab.

Grade 3 or 4 dermatologic toxicities and infectious sequelae (e.g., acneiform rash, mucocutaneous disease etc):

- 1st occurrence, Grade 3/4: delay infusion 1 to 2 weeks; if condition improves, continue at 500mg/m² Q2W. If no improvement, discontinue cetuximab.
- 2nd occurrence, Grade 3/4: delay infusion 1 to 2 weeks; if condition improves, resume treatment at 400mg/m² Q2W. If no improvement, discontinue cetuximab.
- 3rd occurrence, Grade 3/4: delay infusion 1 to 2 weeks; if condition improves, resume treatment at 300mg/m² Q2W. If no improvement, discontinue cetuximab.
- 4th occurrence, Grade 3/4: discontinue cetuximab.
- These recommendations were adapted from the cetuximab label “Recommended Dosage Modifications for Adverse Reactions” table. Management should be individualized according to guidelines used at each participating institution and to the clinical judgement of the Investigator.

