The dose escalation of BMS-986315 in combination with cetuximab (Part 1C) will evaluate the safety and tolerability of escalating doses of BMS-986315 in combination with cetuximab, to determine the combination MTD/RP2D in SCCHN participants. Treatment in Part 1C will be initiated in a staggered manner relative to the BMS-986315 Monotherapy Escalation (Part 1A). Specifically, Part 1C can be initiated upon the decision to escalate when at least 2 BMS-986315 dose levels (the current and 1 higher) in Part 1A have been cleared for safety in accordance with dose escalation rules, after which, dose escalation in Part 1A and Part 1C will proceed in parallel separated by 2 dose levels as indicated above, (see [Section 7.2](#)). At no point will the dose of BMS-986315 administered in combination with cetuximab in Part 1C exceed the highest dose determined to be tolerated in Part 1A. In Part 1C, the dose of BMS-986315 will be escalated, whereas the dose of cetuximab will be fixed at 500mg/m² Q2W. However, if it appears that a planned dose level is associated with an unacceptable frequency of toxicities, then intermediate dose levels, alternative BMS-986315 administration schedules, or de-escalating doses of cetuximab may be evaluated. Specifically, if toxicity attributable solely to cetuximab is found to be in excess as compared to the known toxicity profile of the label dose of 400mg/m² followed by 250mg/m² QW, then a decision may be made to change the cetuximab dosing regimen for all of Part 1C.

The safety and tolerability of BMS-986315 in combination with cetuximab will be evaluated using TITE-BOIN design also used to guide escalation decisions. Additional cohorts of participants will be enrolled in up to 2 dose levels previously cleared for safety. The BMS-986315 in combination with cetuximab PD cohorts, will be implemented in order to gather additional information on pharmacodynamic activity, safety, tolerability, preliminary efficacy and PK in SCCHN participants treated with BMS-986315 in combination with cetuximab. Please refer to [Section 5.1.2.4](#) for additional information on the PD cohorts.

The study consists of 4 periods: Screening, Treatment, Safety Follow-up, and Survival Follow-up (up to 2 years following the EOT of study drug). The duration of the study will be approximately 4 years. The study design schematic is presented in [Figure 5.1-1](#). A detailed schematic for study period and participant flow is presented in [Figure 5.1-2](#).

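### Section 7.4.2.1 gives two incompatible cetuximab instructions after a first Grade 3/4 rash that recovers in Part 1C: resume at a reduced dose, or continue at the full dose.

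*Combined protocol and SAP*

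**What the plan says.** Section 5.1 sets the Part 1C background regimen: "the dose of cetuximab will be fixed at 500mg/m² Q2W". Section 7.4 bars dose reduction of BMS-986315 and nivolumab but allows it for cetuximab: "Cetuximab dose may be reduced due to toxicity as described below". Section 7.4.2 also refers the reader to Section 7.4.2.1 for dose reduction guidance.

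Section 7.4.2.1 then addresses the same event twice.

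- Under the general and prevention heading, the bullet on rash of Grade 3 or greater pauses cetuximab until recovery to Grade 2 or less and adds: "Treatment should be resumed at a reduced dose (see below". It gives no dose and does not distinguish a first event from a later one.
- A separate list follows, headed "Grade 3 or 4 dermatologic toxicities and infectious sequelae (e.g., acneiform rash, mucocutaneous disease etc". Its first entry reads "1st occurrence, Grade 3/4: delay infusion 1 to 2 weeks; if condition improves, continue at 500mg/m² Q2W". Its second reads "2nd occurrence, Grade 3/4: delay infusion 1 to 2 weeks; if condition improves, resume treatment at 400mg/m² Q2W" and its third "3rd occurrence, Grade 3/4: delay infusion 1 to 2 weeks; if condition improves, resume treatment at 300mg/m² Q2W". A fourth event ends cetuximab.

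Under the general instructions, cetuximab stops for good if the rash has not come down to Grade 2 or less within 14 days. The section closes by describing its content as adapted from the cetuximab label and leaving management to institutional guidelines and investigator judgement.

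**The concern.** A participant in Part 1C with a first Grade 3/4 acneiform rash that recovers in time falls under both instructions on the same day. One calls for a lower cetuximab dose. The other calls for no change. The cross-reference in the first leads to a list that contains no reduced dose for a first event.

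The stake is comparability within Part 1C. The primary endpoints in Table 4-1 include the incidence of adverse events and of adverse events leading to discontinuation. Section 5.1.2.3 lets toxicities after the DLT period inform dose level decisions. Section 5.1 allows the cetuximab regimen to be changed for all of Part 1C if toxicity attributable solely to cetuximab is excessive. If sites resume at different doses after the same event, part of the variation in those data reflects how the protocol was read rather than how the combination was tolerated.

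**Working it through.** The plan gives no figure to reproduce here. The check is a comparison of texts, followed by simple arithmetic on size.

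**1. Do both rules reach the same participant?** The general bullet covers any rash of Grade 3 or greater. The list names acneiform rash at Grade 3 or 4. For a first event that recovers within 14 days, both apply.

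| Event (recovered) | General bullet | Occurrence list |
|---|---|---|
| 1st Grade 3/4 | reduced dose, amount not given | 500 mg/m² Q2W |
| 2nd Grade 3/4 | reduced dose, amount not given | 400 mg/m² Q2W |
| 3rd Grade 3/4 | reduced dose, amount not given | 300 mg/m² Q2W |

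The rows for the second and third events can be read together. The row for the first cannot, because 500 mg/m² Q2W is the starting dose.

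**2. Does other text settle it?** No. The opening of Section 7.4.2.1, Section 7.4 and Section 7.4.2 all point back to this same text.

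**3. Does the conflict survive the DLT and discontinuation rules?** Yes, at least for Grade 3. Under Section 5.1.3.5, a Grade 3 cetuximab-related rash that improves by at least one grade within two weeks is not a DLT under the rash criterion, so the participant may resume. For Grade 4, the rules on whether treatment resumes at all are themselves unclear. Section 5.1.3.5 makes Grade 4 cetuximab-related rash a DLT. Section 8.1 requires permanent discontinuation for drug-related events meeting DLT criteria. Section 5.1.3 exempts Grade 3 or 4 acneiform rash in Part 1C from its rule against retreatment after a DLT.

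**4. Size of the dose difference.** Two Q2W infusions fall in each 28-day cycle.

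- List, first event: 2 × 500 = 1000 mg/m² per cycle.
- General bullet: no number is given. Assuming it means a dose on the list, the range is 2 × 400 = 800 to 2 × 300 = 600 mg/m² per cycle.
- Difference: (500 − 400)/500 = 20% to (500 − 300)/500 = 40%.

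If a site used 400 mg/m² after the first event, the entry for the second event would again be 400 mg/m², so the list would bring no further reduction at that point.

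**5. Number who could be affected.** Section 3.2.3 gives 1-17% for Grade 3-4 dermatologic toxicity with cetuximab. Section 5.2 gives up to about 36 + 40 + 40 = 116 participants in Part 1C. Assuming the range carries over to this regimen and population:

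- All of Part 1C: 116 × 0.01 = 1.2 to 116 × 0.17 = 19.7, about 1 to 20.
- Escalation only: 36 × 0.01 = 0.4 to 36 × 0.17 = 6.1, about 0 to 6.

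These are ceilings. Participants whose rash does not recover within 14 days stop cetuximab under the general instructions and never reach the conflict.

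**The case against.** The strongest reply is that the text has a workable reading. The general bullet states no dose and defers to what follows, and the only doses in the section are in the occurrence list. A site that follows the cross-reference reaches an explicit instruction for a first event. The bullet could then be a loose summary of a list that does reduce at the second and third events. This makes wide divergence between sites less likely, but it does not remove the mismatch. Following the list means disregarding the bullet's plain statement that the resumed dose is reduced.

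A second reply is that the section offers recommendations and expressly allows individualised management, so some variation is permitted and would remain after any edit. That is correct and limits what the correction can achieve. Discretion still needs a clear default to depart from, and at the first event there is none.

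A reader might infer three stronger points that the documents do not support.

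- **That DLT counts or DLT attribution are affected.** Under Section 5.1.3.5, a rash is classified by its grade and by whether it improves in time, not by the dose at which cetuximab later resumes. The DLT period is days 1 to 28 and cetuximab is given on days 1 and 15. A day 15 infusion delayed by one to two weeks falls on day 22 to 29, which leaves little or no time in the window for a second qualifying event.
- **That this is the most common severe cetuximab toxicity.** Section 3.2.3 gives 1-17% for dermatologic toxicity and 2-5% for infusion reactions. These ranges overlap, so no ranking follows.
- **That efficacy conclusions are compromised.** Section 10.3.1 plans estimates with confidence intervals, and nothing in the documents shows how far a change in cetuximab dose would move them.

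**Conclusion.** The contradiction is real and lies within one section. After a first Grade 3/4 rash that recovers, the dosing rule cannot be followed as written, and neither the cross-references nor the note on individualised management supplies a single default. The consequence is possible variation between sites in later cetuximab exposure, rash recurrence, discontinuations and adverse event summaries in Part 1C. No sample size, escalation boundary or planned inference changes.

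The numbers above are bounds, not estimates. The count of participants rests on the 1-17% range applying to 500 mg/m² Q2W with BMS-986315 and on Part 1C filling to its ceiling. The dose difference rests on the unstated reduced dose being one of the doses on the list. The correction is worth making because this is an operative dosing instruction for an anticipated toxicity and the remedy is small.

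**What to change.** Reconcile the general bullet and the entry for the first occurrence in Section 7.4.2.1, so that one instruction applies after a first Grade 3/4 rash that has recovered. Which dose applies is for the sponsor to decide, and this review takes no position on it.

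In the same edit, check the result against Section 5.1.3 (exemption of Grade 3 or 4 acneiform rash from the rule against retreatment), Section 5.1.3.5 (rash criteria for a DLT in Part 1C) and Section 8.1 (permanent discontinuation for events meeting DLT criteria), so that they agree on who may resume.

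The cost is a one-line wording correction plus that consistency check. No design parameter or analysis needs to change.
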